5.0 Enrollment/Randomization

Our preliminary estimates from historical electronic health record (EHR) data suggest that approximately 9% of VHVI outpatients are current smokers. This is likely an underestimate in light of the known underascertainment of smoking status in the EHR. This translates into a minimum of 120 unique smokers per month. To maximize subject identification, we will use multiple methods of recruitment. Patients are routinely asked about their smoking status during every visit to the VHVI clinic during intake. Data on existing, identified VHVI smokers will be pulled from the Research Derivative (RD), which will include patients' names, phone numbers, and medical record numbers. These identified smokers will be called by study staff or staff of the Clinical Trials Center (CTC) (up to 10 times per patient) to assess eligibility and interest to join the study. Chart review of eligibility will be done at the time of the call. Interested and eligible patients will be invited to enroll in person either at the VHVI clinic or at the CTC, depending on patient preference and staff availability. Interested patients or their providers may also contact study staff directly based on information contained in study posters that will be displayed throughout the VHVI clinic. As an alternative, staff may also utilize the Electronic Health Record (EHR-StarPanel) to identify VHVI smokers who have clinic appointments and approach these smokers for interest and eligibility in clinic. Chart review would be done prior to approaching the patient. Finally, [name], of the Tobacco Treatment Service (TTS), an inpatient tobacco treatment service that treats patients admitted to VUMC may be used to identify additional potential participants. [name] will assess eligibility of cardiology inpatients, who she treats at the bedside. Patients who screen eligible and are interested will then be approached by study staff. Regardless of recruitment methods, study staff will confirm eligibility and, if appropriate, discuss the informed consent document with the prospective study participant. After agreeing to consent, the participant will complete a standardized questionnaire assessing his or her attitudes regarding personalized smoking cessation therapy. Participants will be randomized in blocks of 10, stratified based on self-reported baseline cigarettes per day.

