The goal of this pilot project is to create infrastructure, establish feasibility, and provide necessary preliminary data to design and conduct a prospective randomized trial comparing tailored smoking cessation treatment to usual care. To accomplish this, we will enroll up to 50 outpatient smokers from the Vanderbilt Heart and Vascular Institute (VHVI). After consent, subjects will complete questionnaires, provide biologic samples, and have nicotine metabolic status determined (nicotine metabolic ratio (NMR)). Subjects will be assigned to either: 1) usual care for smoking cessation or 2) personalized smoking cessation care which incorporates the NMR. Biochemically confirmed abstinence (by exhaled carbon monoxide, using a threshold of < 10 parts per million (ppm)) will be determined at the six month follow up.²⁰ For deliverables, we will: 1) demonstrate capacity to conduct large-scale personalized smoking cessation trials in the clinical environment, and 2) assess patient attitudes regarding personalized smoking treatment.

Aim 1. Develop infrastructure and procedures necessary to conduct a prospective randomized trial comparing tailored smoking cessation treatment to usual care. We hypothesize that we will successfully: 1) enroll outpatient adult daily smokers; 2) collect, process, and store relevant biologic samples; 3) conduct follow-up assessments and accurately ascertain pertinent smoking cessation and patient reported outcome measures.

Aim 2. Assess patient attitudes regarding personalized smoking therapy including: 1) interest in receiving personalized information, and 2) willingness to guide therapy based on personalized data. We hypothesize that a majority (>50%) of subjects will: 1) favorably view receiving personalized smoking information, and 2) express willingness to guide therapy based on personalized data.

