4.0 Inclusion/Exclusion Criteria

Inclusion criteria: Eligible subjects include adult (18 years of age or older) daily smokers who are seen in VHVI outpatient clinic or cardiology inpatients admitted to VUMC. Current smoking is defined as smoking, on average, ≥5 cigarettes per day every day in the month prior to enrollment. Potential subjects must agree to participate and be willing to accept a medication prescription for tobacco cessation. Subjects must be eligible (i.e., no medical contraindications and willing to take) to receive at least two out of three FDA-approved smoking cessation medications (bupropion, varenicline, and NRT). The requirement of eligibility to take at least 2 of 3 FDA approved medications is necessary for this study so that individuals can take advantage of the NMR-driven guidance of a nicotine medication (i.e., NRT for slow metabolizers) vs. a non-nicotine medication (i.e., varenicline or bupropion for fast/normal metabolizers).

Exclusion criteria: In addition to medication contraindications, subjects will be excluded for inability to give informed consent or participate due to serious psychiatric (e.g., psychosis, schizophrenia, hospitalization for psychiatric condition in the past 3 months or change in psychiatric medications in the past 3 months) or cognitive disorder (e.g., dementia, severe mental retardation); receiving palliative or hospice care; pregnant or breastfeeding; no access to a telephone or inability to communicate by telephone; unable to speak and read English. Because levels of nicotine metabolites fall below detection over time we will exclude patients who have been completely abstinent from cigarettes for >3 days.

In order to maximize participant safety, eligibility for medications will be reviewed by three separate members of the study team. Initial screening will be conducted by the study RA at the time of enrollment. Between enrollment and intervention phone call (~1 week) medication eligibility will be reviewed for each participant by the study PI [name] using a detailed chart review. Finally, at the time of intervention phone call, medication eligibility will again be confirmed by the study counsellor, who is a trained smoking counsellor and nurse (RN).

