As described above, subject samples will be processed through ARUP Laboratory as they would for standard clinical care. Results are available within 2-5 days from the time of blood draw. Slow metabolizers will be defined by a NMR <0.31 and fast metabolizers will be defined by a NMR \geq 0.31 .¹³ Once available, subject NMR values will be entered into the study's secure REDCap database by study personnel.

Study Intervention, medication provision and blinding

Medication Costs

All medications accepted by participants at the initial intervention phone call will be provided to participants free of charge. Medications may be shipped to patients free of charge where appropriate. Subjects in the usual care arm who are still smoking at 6 months will have an opportunity to receive a prescription for smoking cessation therapy at the end of study (see below). Participants who wish to receive prescriptions at that point will be responsible for the cost of medications.

Usual Care Group

All subjects, including those assigned to usual care, will receive phone calls from clinical personnel within 1 month of enrollment. In order to minimize inconvenience, subjects will be asked their preferred times to be called at the time of enrollment. With the aid of a written script, staff will provide participants a verbal description of smoking cessation medications they are eligible to take (as determined by study physician), including efficacy and common side effects. If subjects would like to take a smoking cessation medication, they will be allowed to choose from those they are medically able to receive, and the study physician will call in a prescription to an outpatient pharmacy (with which arrangements have been made to have medication costs billed to the study rather than the subject). Regardless of whether subjects choose to receive a prescription for a medication, they will be offered referral to their state Tobacco Quit Line for smoking cessation counselling via an online portal. This portal will track the patient's progress through the quit line process and these data may be collected for research purposes. Verbal instructions will be provided to participants given prescriptions to contact their primary provider and the research study staff (during regular business hours) in case of adverse effects of a medication. They will also be instructed to call 911 if they believe they are having a medical emergency.

Personalized Care Group

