All subjects, including those assigned to personalized care, will receive phone calls from clinical personnel within 1 month of enrollment. In order to minimize inconvenience, subjects will be asked their preferred times to be called at the time of enrollment. Staff contacting subjects in the personalized care group will have access to NMR values when they become available in the study's secure REDCap database. With the aid of a written script, staff will provide participants a personalized (based on NMR) verbal description of smoking cessation medications they are eligible to take (as determined by study physician), including efficacy and common side effects. If subjects would like to take a smoking cessation medication, they will be allowed to choose from those they are medically able to receive, and the study physician will call a prescription into an outpatient pharmacy (with which arrangements have been made to have medication costs billed to the study rather than the subject). Regardless of whether subjects choose to receive a prescription for a medication, they will be offered referral to their state Tobacco Quit Line for smoking cessation counselling via an online portal. This portal will track the patient's progress through the quit line process and these data may be collected for research purposes. Verbal instructions will be provided to participants given prescriptions to contact their primary provider and the research study staff (during regular business hours) in case of adverse effects of a medication. They will also be instructed to call 911 if they believe they are having a medical emergency.

Follow up phone calls

Study RAs will call subjects at approximately 1, 3 and 6 months post-intervention phone call to assess smoking behavior, self-reported adherence, and side effects including neuropsychiatric side effects. Study personnel will make up to 10 calls per follow up at different times of day and days of the week and call subjects' alternate contacts when needed. Participants will receive \$10 for each phone call that they complete.

Single arm crossover for subjects in Usual Care Group

Subjects in the Usual Care Group who are still smoking at 6 month follow up will receive an additional intervention from study staff. With the aid of a written script, staff will provide participants a

	Baseline	1 mo*	3 mo*	6 mo*	2 weeks*
Outcomes					
Demographics	Х				
Smoking behavior	Х	Х	Х	X	Х
Side effect screening	Х	Х	Х		

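### Section 5.0 fixes and discloses a single block size of 10 within strata; with no stated masking of enrolling staff, a small share of assignments could be foreseen (minor)

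*Protocol*

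**What the plan says.** The protocol gives one sentence on how assignments are generated (Section 5.0): "Participants will be randomized in blocks of 10, stratified based on self-reported baseline cigarettes per day". The allocation ratio, the cut-points for cigarettes per day and the number of strata are not given.

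Other parts of the protocol bear on who could use that information:

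- **Arms.** Section 2.0: "Subjects will be assigned to either: 1) usual care for smoking cessation or 2) personalized smoking cessation care". Up to 50 smokers are to be enrolled at one institution.
- **Enrolling staff.** Section 4.0: "Initial screening will be conducted by the study RA at the time of enrollment". Section 5.0 adds that "study staff will confirm eligibility and, if appropriate, discuss the informed consent document". Neither place says whether these staff can see earlier assignments.
- **Intervention staff.** Section 6.0, Personalized Care Group: "Staff contacting subjects in the personalized care group will have access to NMR values when they become available in the study's secure REDCap database". These callers necessarily know the arm.
- **Masking.** A heading in Section 6.0 reads "Study Intervention, medication provision and blinding", but the text under it does not say who is masked.
- **Timing.** Section 4.0 puts the intervention call about 1 week after enrollment; Section 6.0 says within 1 month.
- **Use of the comparison.** Section 10.0 says the pilot is not powered for group differences but will still assess them.

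**The concern.** With permuted blocks of a known size, a stratum's past assignments carry information about the next one. Once five of one arm have been used in a block of 10, the rest of that block is certain. Before that, the arm that is behind is the better guess. Varying the size and not disclosing it removes the certainty.

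The setting gives some room to act on such knowledge. Section 5.0 estimates at least 120 unique smokers per month for a trial of up to 50. Staff work from lists with up to 10 calls per patient, approach patients in clinic, or take inpatient referrals, so they have discretion over whom to pursue and when. If more motivated smokers were pursued when one arm was due, the between-group comparison of cessation would be distorted. Aim 1 is also meant to establish procedures for a later full-scale trial, and allocation is one of them.

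**Working it through.** The protocol states no figure on predictability, so there is none to reproduce.

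**Inputs.** Block size 10 (Section 5.0); two arms and up to 50 subjects (Section 2.0). Assumed: 1:1 allocation, so five of each arm per block, and the splits into strata used below.

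**Step 1. A full block, every earlier assignment seen at once.** Write the block size as 2m, with m = 5.

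- Expected certain assignments = 2m/(m + 1) = 10/6 = 1.67 of 10, or 16.7%.
- Expected correct guesses when always naming the arm that is behind = m + (2^(2m)/C(2m, m) − 1)/2 = 5 + (1024/252 − 1)/2 = 6.53 of 10, or 65.3%.

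The chance that an assignment is certain, by place in the block, is 0 for places 1-5, then 0.8%, 4.8%, 16.7%, 44.4% and 100% for places 6-10. These sum to 1.67.

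**Step 2. Up to 50 subjects, allowing for incomplete last blocks.**

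| Assumed strata | Certain, of 50 | Correct guesses, of 50 |
|---|---|---|
| No partial blocks (e.g. 50, or 30 + 20) | 8.3 (16.7%) | 32.7 (65.3%) |
| 25 + 25 | 6.7 (13.3%) | 31.7 (63.5%) |
| 17 + 17 + 16 | 5.1 (10.2%) | 31.2 (62.4%) |
| 13 + 13 + 12 + 12 | 6.7 (13.3%) | 31.5 (62.9%) |

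**Step 3. Delay.** The arm shows at the intervention call, not at enrollment. If the latest k assignments in the stratum are still unseen, the subject in place j has the predictability that place j − k has without delay. The last k terms of the sum in Step 1 therefore drop out (full blocks):

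- k = 1: (0.0079 + 0.0476 + 0.1667 + 0.4444)/10 = 6.7% certain; 60.3% guessed correctly.
- k = 2: (0.0079 + 0.0476 + 0.1667)/10 = 2.2% certain, about 1 of 50; 58.1% correct.
- k = 3: (0.0079 + 0.0476)/10 = 0.6% certain; 55.9% correct.
- k = 5: none certain; 53.0% correct.

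**Step 4. Other block sizes.** Fixed and known sizes smaller than 10 are worse: size 4 gives 33.3% certain and 70.8% correct; size 6 gives 25.0% and 68.3%.

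For random, undisclosed sizes, simulated with strata of 25 and a guesser who names the arm that is behind:

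| Block sizes | Correct guesses | Mean absolute arm difference at 25 |
|---|---|---|
| Fixed 10 | 63.4% | 1.4 |
| 8/10/12 | 63.7% | 1.3 |
| 6/8/10/12 | 64.4% | 1.2 |
| 4/6/8 | 67.0% | 1.1 |

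The fixed-10 arm difference can be checked by hand. Five subjects remain in an open block, so it is (2 × 5 + 50 × 3 + 200 × 1)/252 = 360/252 = 1.43.

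Varying the size takes away certainty about where a block ends. It does not lower the plain guessing rate, and small mixes raise it.

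**The case against.** The strongest reply is that Steps 1 and 2 assume recruiters see every earlier assignment at once, which the protocol does not say. It gives the intervention call to a counsellor about a week to a month after enrollment, and Step 3 shows that two or three pending enrollments almost remove the certain assignments. The research assistants' later calls cover smoking, adherence and side effects. Both arms choose among the medications they are eligible for, so drug use does not reveal the arm. The usual-care crossover does reveal it, but only at 6 months. This reply stands, and it is why the size is given as an upper bound.

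A reader might also infer that recruiters know the stratum, and so the relevant tally, before approaching anyone. The text does not establish that. Eligibility needs only an average of at least 5 cigarettes per day, smoking intensity is in the survey given at enrollment, and the cut-points are not stated.

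Two further points have weight. A block of 10 is already less predictable than a smaller fixed block. And who holds the list and how assignments are released may be set out in a document not shown, so silence on those mechanics alone is not a fault. What remains is a choice the protocol does state: one constant block size, disclosed.

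Finally, this is an unpowered feasibility pilot, and Section 5.0 describes the attitude questionnaire before it mentions randomization. That limits the consequence to the exploratory comparison of arms.

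**Conclusion.** The point holds in a limited form. Section 5.0 fixes and prints one block size within strata, at one institution, where intervention staff know the arm and no masking of enrolling staff is stated. Under 1:1 allocation and immediate sight of all earlier assignments, at most about 10-17% of assignments (5 to 8 of 50) could be known and about 62-65% guessed correctly. With two or three assignments unseen, the certain share is about 2% or less. How many would be pending in practice is not known.

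A reader might infer that staff can know many upcoming assignments, or that enrollment will be steered. The documents support neither: sight of the running tally by recruiters is neither stated nor excluded, and steering is only a possibility. It is a modest, avoidable risk to the exploratory between-group comparison. Priority: minor, for consideration.

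**What to change.** In Section 5.0, replace the fixed block size with randomly permuted blocks of randomly varying size within each cigarettes-per-day stratum. Leave the sizes out of the protocol, known only to whoever prepares the list. Choose sizes not much smaller than 10, for example a mix of 8/10/12 or 6/8/10/12, because small mixes such as 4/6/8 raise the guessing rate to about 67%.

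Add that each assignment is released only after consent and the baseline survey are complete, to the intervention counsellor and not to recruiting staff. This second part gives the main protection, since varying the sizes alone leaves a running-balance guess right about 64% of the time.

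The cost is a short change to Section 5.0 and a new allocation list in the REDCap database already in use. No extra subjects or visits are needed, and end-of-stratum balance is not worse (mean arm difference about 1.2 for 6/8/10/12 against 1.4 for fixed 10, at 25 subjects).

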6.0 Study Procedures

Baseline Data Collection

Upon enrollment patients will be given an initial survey detailing smoking history, smoking related traits (e.g. smoking intensity, measures of addiction, prior quit attempts, use of other tobacco products), and attitudes regarding personalized medicine. Participants will be compensated \$10 for their completion of the survey.

Biospecimen collection, processing, and storage

To minimize risk, a total of 30 mL (well below the accepted cutoff of 50 mL for "minimal risk") of whole blood will be collected into 3 EDTA coated tubes (lavender top vacutainers), labeled appropriately, placed on ice. Two tubes will be transported to the laboratory space of [name] to be immediately processed by centrifugation. The plasma fraction will be aliquoted into storage vials and stored at -80°C in temperature monitored freezers located on the 12th floor MRBIV. [name] has dedicated space and personnel housed in the lab of [name], Professor of Medicine and Pharmacology and Assistant Vice-Chancellor for Personalized Medicine. The Lab consists of ~2,000 contiguous square feet and includes all equipment, supplies, and personnel required for sample processing and storage. The third blood sample (~10 mL) will be collected in an EDTA coated vial and transferred to the VUMC reference laboratory for measurement of nicotine, cotinine, 3-OH-cotinine. The VUMC laboratory currently contracts with ARUP national reference laboratory, which conducts this assay using quantitative high performance liquid chromatography-tandem mass spectrometry using CLIA approved protocols and quality control. Results are reported within 2-5 days from sample collection. (http://ltd.aruplab.com/tests/pub/0092361) At approximately 1 month, a subset of participants will be selected to follow up in person, where they will have up to 10 mL of blood drawn to biochemically assess adherence by measurement of smoking cessation drug levels. These samples will be shipped to the laboratory of [name] at the University of Toronto, Canada, where drug and metabolite levels will be measured using established assays.

Nicotine metabolite ratio (NMR) measurement

As described above, subject samples will be processed through ARUP Laboratory as they would for standard clinical care. Results are available within 2-5 days from the time of blood draw. Slow metabolizers will be defined by a NMR <0.31 and fast metabolizers will be defined by a NMR \geq 0.31 .¹³ Once available, subject NMR values will be entered into the study's secure REDCap database by study personnel.

Study Intervention, medication provision and blinding

Medication Costs

All medications accepted by participants at the initial intervention phone call will be provided to participants free of charge. Medications may be shipped to patients free of charge where appropriate. Subjects in the usual care arm who are still smoking at 6 months will have an opportunity to receive a prescription for smoking cessation therapy at the end of study (see below). Participants who wish to receive prescriptions at that point will be responsible for the cost of medications.

Usual Care Group

All subjects, including those assigned to usual care, will receive phone calls from clinical personnel within 1 month of enrollment. In order to minimize inconvenience, subjects will be asked their preferred times to be called at the time of enrollment. With the aid of a written script, staff will provide participants a verbal description of smoking cessation medications they are eligible to take (as determined by study physician), including efficacy and common side effects. If subjects would like to take a smoking cessation medication, they will be allowed to choose from those they are medically able to receive, and the study physician will call in a prescription to an outpatient pharmacy (with which arrangements have been made to have medication costs billed to the study rather than the subject). Regardless of whether subjects choose to receive a prescription for a medication, they will be offered referral to their state Tobacco Quit Line for smoking cessation counselling via an online portal. This portal will track the patient's progress through the quit line process and these data may be collected for research purposes. Verbal instructions will be provided to participants given prescriptions to contact their primary provider and the research study staff (during regular business hours) in case of adverse effects of a medication. They will also be instructed to call 911 if they believe they are having a medical emergency.

Personalized Care Group

All subjects, including those assigned to personalized care, will receive phone calls from clinical personnel within 1 month of enrollment. In order to minimize inconvenience, subjects will be asked their preferred times to be called at the time of enrollment. Staff contacting subjects in the personalized care group will have access to NMR values when they become available in the study's secure REDCap database. With the aid of a written script, staff will provide participants a personalized (based on NMR) verbal description of smoking cessation medications they are eligible to take (as determined by study physician), including efficacy and common side effects. If subjects would like to take a smoking cessation medication, they will be allowed to choose from those they are medically able to receive, and the study physician will call a prescription into an outpatient pharmacy (with which arrangements have been made to have medication costs billed to the study rather than the subject). Regardless of whether subjects choose to receive a prescription for a medication, they will be offered referral to their state Tobacco Quit Line for smoking cessation counselling via an online portal. This portal will track the patient's progress through the quit line process and these data may be collected for research purposes. Verbal instructions will be provided to participants given prescriptions to contact their primary provider and the research study staff (during regular business hours) in case of adverse effects of a medication. They will also be instructed to call 911 if they believe they are having a medical emergency.

Follow up phone calls

Study RAs will call subjects at approximately 1, 3 and 6 months post-intervention phone call to assess smoking behavior, self-reported adherence, and side effects including neuropsychiatric side effects. Study personnel will make up to 10 calls per follow up at different times of day and days of the week and call subjects' alternate contacts when needed. Participants will receive \$10 for each phone call that they complete.

Single arm crossover for subjects in Usual Care Group

Subjects in the Usual Care Group who are still smoking at 6 month follow up will receive an additional intervention from study staff. With the aid of a written script, staff will provide participants a

	Baseline	1 mo*	3 mo*	6 mo*	2 weeks*
Outcomes					
Demographics	Х				
Smoking behavior	Х	Х	Х	X	Х
Side effect screening	Х	Х	Х		
Attitudes & Beliefs	Х			Х	
Patient satisfaction				Х	
Biochemical validation of cessation				X	
Biochemical validation of adherence (subset of participants)		X			
Medication use		Х	Х		Х

NMR) verbal description of smoking cessation medications they are eligible to take (as determined by study physician), including efficacy and common side effects. If subjects would like to take a smoking cessation medication, they will be allowed to choose from those they are medically able to receive, and a prescription will be called into an outpatient pharmacy by the study physician. The intent of this design is to assess the impact of a personalized message on medication uptake in

personalized (based on

Relative to 6-month follow-up (applies to subjects who are still smoking in Usual Care)

participants who failed to guit with the usual care treatment. The cost of medications will be the responsibility of participants who chose to have prescriptions filled. Participants provided prescriptions will be called by study staff in approximately 2 weeks to assess whether they have filled their prescriptions and are taking the medication.

EHR data collection

Prospective participants who are identified smokers in the VHVI clinic will have their EHR examined by study staff to determine eligibility, and EHR data collected in the screening form will be retained for future analysis. For enrolled participants, research staff will review the participant's EHR to collect relevant clinical data. Staff may review participant records for up to 5 years after enrollment.

Outcome assessment

Subject outcomes will be assessed by phone approximately 1, 3 and 6 months post-intervention phone call. At follow up, a research assistant will complete interviews assessing smoking behavior, self-reported side effects, and measures of patient engagement and attitudes toward precision medicine. At approximately 1 month, a subset of participants will be selected to complete follow-up in person, where, in addition to an interview, they will have blood drawn to biochemically assess adherence by measurement of smoking cessation drug levels. Subjects will receive an additional \$10 for completing 1 month follow up in person. At approximately 6 months, subject outcomes may be assessed in person. Subjects self-reporting abstinence may have smoking status confirmed biochemically using end expired carbon monoxide. Biochemically validated abstinence will be defined as end expired carbon monoxide less than 10 ppm. Participants will receive \$10 for each of these completed calls and an additional \$10 if they participate in an end-expired carbon monoxide test at 6 months. This will be sent by mail in the form of a check. Participants in the single arm crossover group (i.e., those in the Usual Care group who were still smoking at 6 months) who accepted medication prescriptions will receive phone calls approximately 2 weeks after the second personalized intervention to assess whether they have filled the prescription. The most any one participant can be compensated (completing all surveys, the additional blood draw and biochemical validation) is \$60.00 over the course of approximately 6 months.

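### The single-arm crossover cannot isolate the impact of the personalized message on uptake, because payer and offer number change with the message and nobody receives a repeat generic offer

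*Protocol*

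**What the plan says.** All of this is in Section 6.0 of the protocol.

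- **First offer, usual care.** "All subjects, including those assigned to usual care, will receive phone calls from clinical personnel within 1 month of enrollment". The same window applies to the personalized arm. Usual-care participants hear a scripted description of their eligible medications that does not draw on the nicotine metabolite ratio (NMR). On payment: "All medications accepted by participants at the initial intervention phone call will be provided to participants free of charge".
- **Second offer, usual care only.** Those still smoking at the 6-month follow-up hear an NMR-based description. On payment: "The cost of medications will be the responsibility of participants who chose to have prescriptions filled". The Medication Costs paragraph agrees: "Participants who wish to receive prescriptions at that point will be responsible for the cost of medications".
- **Purpose.** "The intent of this design is to assess the impact of a personalized message on medication uptake in" people who did not quit under usual care.
- **Measurement.** "Participants provided prescriptions will be called by study staff in approximately 2 weeks to assess whether they have filled their prescriptions". The call also asks about current use. The schedule table also lists medication use at 1 and 3 months after the first call. It has no row for whether a prescription was accepted.

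Section 10.0 says that the pilot is not powered and that analyses will be descriptive and exploratory, with some assessment of between-group differences. It does not mention the crossover.

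**The concern.** The stated purpose is causal: it asks what the message does to uptake. Answering that needs a comparison in which the message differs and the other influences on uptake do not. Here the message arrives together with a change of payer and a change from first to repeat offer, and no group holds those two fixed.

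The pilot is meant to supply preliminary data for a full trial. If few participants fill the second prescription, that could be held against personalization when cost was the reason. If many do, personalization could be credited when a second prompt, or 6 more months of smoking, was the reason. Being descriptive and unpowered excuses imprecision. It does not make an uncontrolled proportion into the impact of a message.

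**Working it through.** The protocol gives no sample size, effect or precision for the crossover, so there is no figure to reproduce. The check is which comparisons the design makes available.

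**Step 1. Possible comparators for second-offer uptake.**

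| Comparator | Message | Payer | Offer number | Isolates the message? |
|---|---|---|---|---|
| Usual care, first offer | differs | differs | differs | No |
| Personalized arm, first offer | same type | differs | differs | No |
| Personalized arm, still smoking at 6 months | – | – | – | No second offer is described |
| Usual care, repeat generic self-paid offer | – | – | – | Nobody receives one |

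The one contrast in which the message differs and payer, offer number and call window do not is the randomised first call: usual care against personalized care, both study-paid, both within 1 month of enrollment.

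**Step 2. Why the sign could mislead (assumed values only).** Suppose a reader set second-offer uptake against an assumed first-offer uptake of 60%, and payment plus repetition multiplied uptake by m.

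- m = 0.7, no message effect: 0.60 × 0.7 = 0.42, an apparent change of −18 points.
- m = 0.7, true message effect +15 points: 0.75 × 0.7 = 0.525, an apparent change of −7.5 points.
- m = 1.1, no message effect: 0.60 × 1.1 = 0.66, an apparent change of +6 points.

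The documents give no value for m. These lines show only that the direction is not protected.

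**Step 3. Size of the crossover group.** Inputs: up to 50 enrolled (Section 2.0); 1:1 allocation (assumed, the ratio is not stated), so 25 in usual care; 5% to 25% no longer smoking at 6 months. That range combines the low end of a 6-month unaided rate with a one-year treated rate, both from Section 2.0, and full follow-up is assumed.

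- 25 × (1 − 0.25) = 18.75, about 19; 25 × (1 − 0.05) = 23.75, about 24.
- Exact 95% CI for uptake near one half: 10/19 gives 29 to 76%; 12/24 gives 29 to 71%.

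**Step 4. Selection, if first and second offers were compared.** With first-offer uptake u and quit rates q1 in takers and q0 in non-takers, first-offer uptake among those still smoking is u(1 − q1) / [u(1 − q1) + (1 − u)(1 − q0)]. Take u = 0.60 (assumed) and q1 = 0.25.

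- q0 = 0.10: 0.45 / (0.45 + 0.36) = 0.556, which is 4.4 points below u.
- q0 = 0.05: 0.45 / (0.45 + 0.38) = 0.542, which is 5.8 points below u. This pair implies a fivefold ratio, wider than the 1.5 to 3-fold in Section 2.0, so it is generous to the concern.

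**Step 5. Precision of the randomised first-call contrast.** Half-width = 1.96 × √(2p(1 − p)/n), with n per arm of 25, or 20 if only 40 enrol (assumed).

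- n = 25: p = 0.5 gives 1.96 × √0.0200 = 0.277; p = 0.8 gives 1.96 × √0.0128 = 0.222.
- n = 20: p = 0.5 gives 1.96 × √0.0250 = 0.310; p = 0.8 gives 1.96 × √0.0160 = 0.248.

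**Step 6. Adding the missing control here.** Randomising 19 to 24 remaining smokers to a generic or personalized repeat offer gives 9.5 to 12 per group. The half-width at p = 0.5 is 1.96 × √(0.5/9.5) = 0.450 to 1.96 × √(0.5/12) = 0.400. Power for 30% against 50% uptake is 14 to 16% (two-sided 5%); 80% power would need 93 per group.

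**The case against.** The strongest reply is that the protocol promises very little. It openly calls the crossover single-arm, places it at the end of the study, attaches no estimand or test to it, and never says that second-offer uptake will be compared with first-offer uptake. On this view the whole point hangs on one word, impact, and a SAP may settle the analysis. Much of this stands, and it is why the point is minor. It does not remove the point. That sentence is the only purpose given for the crossover, and no SAP can supply a comparator that no participant receives.

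Three stronger readings are tempting, and the documents do not support them.

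- **That selection on still smoking is a flaw in itself.** The same sentence names people who failed usual care as the population of interest. Selection distorts only a comparison with first-offer uptake in the arm, which the protocol does not specify, and Step 4 puts it at about 4 to 6 points.
- **That the 2-week call uses the wrong denominator.** The call goes to those "who accepted medication prescriptions will receive phone calls approximately 2 weeks after the second personalized intervention to assess whether they have filled the prescription". Decliners have no study prescription to fill, and nothing makes acceptors the denominator.
- **That the measurement windows are mismatched.** The windows do differ (2 weeks against 1 and 3 months), but this too matters only for a first-to-second comparison.

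One might add that cost need not affect accepting a prescription. That is fair for acceptance. But filling and taking, which the 2-week call measures, is where cost acts most directly, and repetition affects both.

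**Conclusion.** The stated intent is wrong as written, and the point is minor. The crossover can describe uptake of a second, personalized, self-paid offer. It cannot show the impact of the message, because payer and offer number change with it and no repeat generic offer exists on the same terms. This rests on the protocol's text alone and needs none of the assumed rates.

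The size of any distortion is unknown. The precision figures assume 1:1 allocation, 20 to 25 per arm and 50 to 80% uptake. A reader should not infer that the randomised comparison, either aim or the feasibility results are compromised: the crossover follows the 6-month assessment and lies outside both aims.

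**What to change.** - **Reword the intent in Section 6.0**: the crossover describes uptake of a second, personalized, self-paid offer in usual-care participants still smoking at 6 months.
- **Report two proportions, each among all those offered, with 95% CIs**: those who accept a prescription, and those who have filled it and are taking the medication at about 2 weeks. Label both uncontrolled and do not attribute them to personalization.
- **Take any message effect on uptake from the randomised first-call comparison**: medication use at 1 and 3 months, plus prescription acceptance, as a between-arm difference with a 95% CI. Section 10.0 already foresees assessing between-group differences.
- **Leave the effect in people who failed usual care to the full trial.** It needs a repeat generic offer on equal payment terms, and the numbers here are too small to be useful (Step 6).

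The cost is one reworded sentence, one table and one added data item. Acceptance is not in the schedule table and must be recorded for both offers; since the study physician calls in each prescription, study prescription records can supply it. The downside is that the crossover can no longer be presented as showing an effect of personalization, and the substitute estimate is imprecise and limited to first offers.
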